| 8.3 Potential Benefits of Participation in the DEVICE Trial | 17 | |
| 8.4 Minimization of Risk | 18 | |
| | | |

2

| 9 Statistical Considerations | | |
|--|----|--|
| 9.1 General Considerations | 18 | |
| 9.2 Sample Size Estimation | 18 | |
| 9.3 Analysis Populations | 19 | |
| 9.4 Statistical Analysis | 19 | |
| 9.4.1 Primary Analysis | 19 | |
| 9.4.2 Secondary Analyses | 19 | |
| 9.4.4 Handling of Missing Data | 20 | |
| 9.4.5 Interim Analysis | 20 | |
| 10 Privacy and Confidentiality | | |
| 11 Follow-up and Record Retention | | |
| 12 Safety Monitoring and Adverse Events | | |
| 12.1 Adverse Event Definitions | | |
| 12.2 Monitoring for Adverse Events | | |
| 12.3 Recording and Reporting Adverse Events | | |
| 12.4 Clinical Outcomes that may be Exempt from Adverse Event Recording and Reporting | | |
| 12.5 Unanticipated Problems involving Risks to Subjects or Others | | |
| 13 Data and Safety Monitoring Board (DSMB) | | |
| 14 References | 26 | |

Trial Summary

| Title | DirEct Versus VIdeo LaryngosCopE Trial (DEVICE) | |
|--------------------|--|--|
| Background | Clinicians perform rapid sequence induction, laryngoscopy, and tracheal intubation for more than 5 million critically ill adults as a part of clinical care each year in the United States. Failure to intubate the trachea on the first attempt occurs in more than 10% of all tracheal intubation procedures performed in the emergency department (ED) and intensive care unit (ICU). Improving clinicians rate of intubation on the first attempt could reduce the risk of serious procedural complications. | |
| | In current clinical practice, two classes of laryngoscopes are commonly used to help clinicians view the larynx while intubating the trachea: a video laryngoscope (equipped with a camera and a video screen) and a direct laryngoscope (not equipped with a camera or video screen). For every laryngoscopy and intubation procedure performed in current clinical practice, clinicians use either a video or a direct laryngoscope. Prior research has shown that use of a video laryngoscope improves the operator's view of the larynx compared to a direct laryngoscope. Whether use of a video laryngoscope increases the likelihood of successful intubation on the first attempt remains uncertain. A better understanding of the comparative effectiveness of these two common, standard-of-care approaches to laryngoscopy and intubation could improve the care clinicians deliver and patient outcomes. | |
| Study Design | Multi-center, parallel-group, non-blinded, randomized clinical trial | |
| Trial Groups | Video laryngoscope group Direct laryngoscope group | |
| Inclusion Criteria | Patient is located in a participating unit Planned procedure is orotracheal intubation using a laryngoscope Planned operator is a clinician expected to routinely perform tracheal intubation in the participating unit | |
| Exclusion Criteria | Patient is known to be less than 18 years old Patient is known to be pregnant Patient is known to be a prisoner Immediate need for tracheal intubation precludes safe performance of study procedures Operator has determined that use of a video laryngoscope or use of a direct laryngoscope is required or contraindicated for the optimal care of the patient | |
| Risks | Participation in this study involves minimal incremental risk because: | |

| r | | |
|-------------------------|--|--|
| | All patients eligible for the study are already undergoing tracheal intubation with a video laryngoscope or a direct laryngoscope as part of their clinical care Use of a video laryngoscope and use of a direct laryngoscope are the most common approaches to tracheal intubation of critically ill adults in clinical care No benefits or risks are currently known to differ between the two approaches If clinicians determine either approach to be required or contraindicated for the optimal care of an individual patient, the patient is excluded from the study | |
| Benefits | The benefits of the DEVICE trial are largely the indirect benefits to future patients that will result by a better understanding of whether use of video laryngoscope or use of a direct laryngoscope is found to prevent complications. | |
| Consent | The trial will be conducted with waiver of informed consent because: Participation in the study involves minimal incremental risk Obtaining informed consent prior to emergency tracheal intubation of critically ill adults is impracticable | |
| Randomization | Using opaque envelopes available in participating units, participants will be randomized 1:1 to either use of a video laryngoscope or use of a direct laryngoscope on the first laryngoscopy attempt. Randomization will be completed in permuted blocks of variable size and stratified by site. | |
| Primary Outcome | Successful intubation on the first attempt , defined as the placement of an endotracheal tube in the trachea with a single insertion of a laryngoscope blade into the mouth and EITHER a single insertion of an endotracheal tube into the mouth OR a single insertion of a bougie into the mouth followed by a single insertion of an endotracheal tube over the bougie into the mouth. | |
| Secondary Outcome | Incidence of severe complications , defined as the occurrence of one or more of the following between induction and 2 minutes after intubation: [1] severe hypoxemia (SpO2 <80%), [2] severe hypotension (systolic blood pressure <65 mm Hg or new or increased vasopressor administration), [3] cardiac arrest not resulting in death within 1 hour of induction, or [4] cardiac arrest resulting in death within 1 hour of induction. | |
| Exploratory Outcomes | Procedural: Duration from laryngoscopy to tracheal intubation – defined as the interval (in seconds) between insertion of the laryngoscope into the mouth on the first laryngoscopy attempt and final placement of an endotracheal tube or tracheostomy tube in the trachea. Number of laryngoscopy attempts | |

| | Number of attempts to cannulate the trachea with a bougie Number of attempts to cannulate the trachea with an endotracheal tube Reason for failure to intubate on the first attempt Operator-reported aspiration into the airway Safety: Esophageal intubation Injury to the teeth Clinical: ICU-free days in the first 28 days Ventilator free days in the first 28 days 28-day, all-cause in-hospital mortality | |
|-------------------|---|--|
| Analysis | The primary analysis will be an intention-to-treat comparison of patients randomized to the video laryngoscope group versus patients randomized to the direct laryngoscope group with regard to the primary outcome of successful intubation on the first attempt. The difference in proportion and the associated 95% confidence interval will be presented. Between group differences will be examined using a Chi-square test. | |
| Sample Size | 2,000 patients | |
| Expected Duration | 18 months | |

1 Background

Clinicians frequently perform tracheal intubation of critically ill patients in the emergency department (ED) or intensive care unit (ICU). In 10-20% of emergency tracheal intubations, clinicians are unable intubate the trachea on the first attempt, which increases the risk of peri-intubation complications.^{1–4} Successful laryngoscopy and tracheal intubation requires using a laryngoscope to [1] visualize the larynx and vocal cords and [2] create a pathway through which an endotracheal tube can be advanced through the oropharynx and larynx and into the trachea.

In current clinical practice, two classes of laryngoscopes are commonly used by clinicians to view the larynx while intubating the trachea: a video laryngoscope (equipped with a camera and a video screen) and a direct laryngoscope (not equipped with a camera or video screen). Clinicians use either a video laryngoscope or a direct laryngoscope as standard of care for every laryngoscopy and intubation procedure performed in current clinical practice.

Direct Laryngoscope. The Macintosh direct laryngoscope (Fig. 1) consists of a battery-containing handle and a blade with a light source. The operator achieves a direct line of sight –from the operator's eye through the mouth to the larynx and trachea – by using the laryngoscope blade to displace the tongue and elevate the epiglottis.^{5,6}

Video Laryngoscope. Video laryngoscopes consist of a fiberoptic camera and light source near the tip of the laryngoscope blade, which transmits images to a video screen (Fig. 2). The position of the camera near the tip of the laryngoscope blade facilitates visualization of the larynx and trachea.

Use of a video laryngoscope and use of a direct laryngoscope are both common, standard-of-care approaches the clinicians use to perform tracheal intubation in the ED and ICU in current clinical care.

Figure 1. Macinosh direct laryngoscope creating a direct line-of-sight to the airway opening (from: Walls Manual of Emergency Airway Management, 5th ed. 2018).

Figure 2. Example of a video laryngoscope with standard geometry blade (C-MAC with pocket monitor, Karl Storz Inc).

Currently, it is unknown whether use of a video laryngoscope or use of a direct laryngoscope has any effect on successful intubation on the first attempt or any other outcome. Some prior research has raised the hypothesis that using a video laryngoscope would increase clinicians' rate of successful intubation on the first attempt by facilitating the view of the larynx.⁷ Some prior research has raised the hypothesis that using a direct laryngoscope would increase clinicians' rate of successful intubation on the first attempt by facilitating the view of the larynx.⁷ Some prior research has raised the hypothesis that using a direct laryngoscope would increase clinicians' rate of successful intubation on the first attempt by facilitating a clear pathway for placement of the tube through the mouth into the trachea.

To date, 8 small single-center randomized trials^{8–15} and one 371-patient multicenter randomized clinical trial¹⁶ have been conducted under waiver of or alteration of informed consent to compare use of a video vs a direct laryngoscope in the setting of emergency tracheal intubation in the ED or ICU. Two of these trials provide the most direct preliminary data for this proposal. The "Facilitating EndotracheaL intubation by Laryngoscopy technique and apneic Oxygenation Within the ICU (FELLOW)" randomized clinical trial, conducted under waiver of informed consent, compared these two standard-of-

care approaches during 150 emergency tracheal intubations at Vanderbilt University Medical Center, finding no difference in the rate of successful intubation on the first attempt between use of a video and use of a direct laryngoscope.¹¹ The "McGrath Mac Videolaryngoscope Versus Macintosh Laryngoscope for Orotracheal Intubation in the Critical Care Unit (MACMAN)" randomized clinical trial among 371 critically ill adults found no difference between use of a video vs direct laryngoscope in the rate of successful intubation on the first attempt. However, a hypothesis-forming post-hoc exploratory analysis of peri-intubation complications suggested that use of a video laryngoscope may be associated with a higher rate of complications than direct laryngoscope (9.5% vs 2.8%, respectively, p=0.01).¹⁶ These trials were underpowered to rule out small but clinically significant differences in first pass success, and were limited to intubations performed by inexperienced trainees in one practice setting (intensive care units), but they demonstrated hypothesis-generating findings requiring validation in larger trials that reflect the full spectrum of settings, operator specialties, and operator experience levels in which emergency tracheal intubation is routinely performed.

Because of the imperative to optimize emergency tracheal intubation in clinical care, the common use of both video and direct laryngoscopes in current clinical practice, and the lack of definitive data from randomized trials to definitively inform whether use of a video laryngoscope or a direct laryngoscope effects the rate of successful intubation on the first attempt, examining whether one approach increases the odds of successful intubation on the first attempt represents an urgent research priority. To address this knowledge gap, we propose to conduct a large, multicenter, randomized clinical trial comparing use of a video laryngoscope versus use of a direct laryngoscope with regard to successful intubation on the first attempt among critically ill adults undergoing tracheal intubation in the ED or ICU.

2 Aims, Hypotheses, and Study Description

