9.4.2 Secondary Analyses

We will perform:

- 1. Intention-to-treat comparisons of secondary, exploratory, and safety outcomes; and
- 2. Intention-to-treat comparison of the primary outcome between groups using a generalized linear mixed effects model including a random effect for site and fixed effects for group assignment and pre-specified baseline variables, including: age; sex; body mass index; and location at enrollment (ED or ICU).

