induction and the first attempt at laryngoscopy, time of start of first laryngoscopy attempt, laryngoscope used on first attempt (model, blade size, blade shape), use of video screen (if applicable) on the first laryngoscopy attempt, best Cormack-Lehane grade of view³⁵ on the first laryngoscopy attempt, presence of body fluid obstructing view of the larynx, presence of upper airway obstruction or edema, number of intubation attempts (number of times the laryngoscope entered the mouth, number of times the bougie entered mouth [if applicable], number of times the endotracheal tube entered the mouth), reason for failure of the first intubation attempt (if applicable), procedural adjustments made for the final intubation attempt, esophageal intubation, injury to teeth, operator-reported pulmonary aspiration between induction and intubation, time of successful tracheal intubation, endotracheal tube size, lowest SpO₂ from induction until 2 minutes after intubation, lowest systolic blood pressure from induction until 2 minutes after intubation, new or increased vasopressor administration from induction until 2 minutes after intubation, cardiac arrest from induction until 2 minutes after intubation not resulting in death within 1 hour of induction, cardiac arrest from induction until 2 minutes after intubation resulting in death within 1 hour of induction.

- 3. 24 hours after enrollment: new pneumothorax detected in the first 24 hours after induction, vasopressor receipt at 24 hours after induction, SpO₂ at 24 hours after induction, FIO₂ at 24 hours after induction, positive end-expiratory pressure (PEEP) at 24 hours after induction, systolic blood pressure at 24 hours after induction.
- 4. In-Hospital Outcomes: Ventilator-free days in the first 28 days, ICU-free days in the first 28 days, and in-hospital mortality at 28 days. Definitions for ICU-free days and ventilator-free days are provided in the supplementary file, sections 3 and 4.

Primary Outcome

The primary outcome is successful intubation on the first attempt. Successful intubation

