Data for the assessment of the primary outcome are collected by a trained independent observer using a structured data collection form that records the number of insertions of the laryngoscope blade, bougie (if used), and endotracheal tube into the patient's mouth. In the event that data from the independent observer are missing, data from the operator's self-report of successful intubation on the first attempt will be used.

Secondary Outcome

The secondary outcome is the incidence of severe complications occurring between induction and 2 minutes following successful intubation. Severe complications are defined as one or more of the following:

- Severe hypoxemia (lowest oxygen saturation measured by pulse oximetry < 80%);
- Severe hypotension (systolic blood pressure < 65 mm Hg or new or increased vasopressor administration);
- Cardiac arrest not resulting in death
- Cardiac arrest resulting in death

Cardiac arrest will be considered to have resulted in death if a patient who experienced cardiac arrest between induction and 2 minutes after intubation died within the 1 hour following intubation.

Exploratory procedural outcomes are as follows:

- Duration of laryngoscopy and tracheal intubation. This is defined as the interval (in seconds) between the first insertion of a laryngoscope blade into the mouth and the final placement of an endotracheal tube or tracheostomy tube in the trachea.
- Number of laryngoscopy attempts
- Number of attempts to cannulate the trachea with a bougie or endotracheal tube
- Successful intubation on the first attempt without a severe complication
- Reason for failure to intubate the trachea on the first attempt, which include:
 - Inadequate view of the larynx
 - o Inability to intubate the trachea with an endotracheal tube
 - Inability to cannulate the trachea with a bougie
 - Attempt aborted due to a change in patient condition (e.g. worsened hypoxemia, hypotension, bradycardia, vomiting, bleeding)
 - Technical failure of the laryngoscope (e.g. battery, light source, camera, screen)
 - Other
- Operator-reported aspiration

Exploratory safety outcomes are as follows:

- Esophageal intubation
- Injury to the teeth

Exploratory clinical outcomes are as follows:

- ICU-free days in the first 28 days
- Ventilator-free days in the first 28 days
- 28-day all-cause in-hospital mortality

Sample Size Estimation

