Analyses will be conducted following reproducible research principles using R (R Foundation for Statistical Computing, Vienna, Austria).⁴⁰ We will present summary tabulations by treatment group. For categorical variables, the number and proportion of patients will be presented. For continuous variables, the mean and standard deviation or median and interquartile range will be presented, as appropriate.

We will analyze a single pre-specified primary outcome and a single pre-specified secondary outcome using a chi-square test. Consistent with recommendations of the Food and Drug Administration⁴¹ and the European Medicines Agency⁴², each will be tested using a two-sided P value with a significance level of 0.05. The primary analysis will occur in an intent-to-treat fashion among all patients randomized, excluding only those patients whose data was withdrawn from the study. For all other analyses except safety analyses, emphasis will be placed on the estimate of effect size with 95% confidence intervals, as recommended by the *International Committee of Medical Journal Editors*⁴³, and no corrections for multiple comparisons will be performed.

Main Analysis of the Primary Outcome

The main analysis will be an unadjusted, intention-to-treat comparison of successful intubation on the first attempt between patients randomized to the video laryngoscope group and patients randomized to the direct laryngoscope group, using a chi-square test. The difference in proportions, the associated 95% confidence interval, and a p value for the primary outcome will be presented.

Secondary Analyses of the Primary Outcome

Multivariable modeling to account for covariates

To account for relevant covariates, we will develop a generalized linear mixed effects model using a logit link function with the primary outcome as the dependent variable, study site as a random effect, and fixed effects of study group and the following pre-specified baseline covariates: age, sex, body-mass index, operator experience quantified as the operator's total number of prior intubations, and location of intubation (ED vs ICU). All continuous variables will be modeled assuming a nonlinear relationship to the outcome using restricted cubic splines with between 3 and 5 knots.

Effect Modification

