Sensitivity Analyses of the Primary Outcome

We will assess the robustness of the findings of the primary analysis in a number of sensitivity analyses. First, because operators may choose to deviate from the assigned laryngoscope for the safety of the patient, we will repeat the primary analysis, but will consider patients for whom the operator crossed over on the first attempt from the assigned laryngoscope type to the non-assigned laryngoscope type not to have experienced successful intubation on the first attempt. Second, we will repeat the primary analysis among only patients

for whom data on the primary outcome from the independent observer is available (i.e., excluding cases in which operator self-report was the sole source of information for the primary outcome). Third, because the operator's prior experience with each type of laryngoscope may affect the likelihood of success with a video laryngoscope compared with a direct laryngoscope, we will repeat the primary analysis among only cases in which the proportion of prior intubations the operator has performed using a direct laryngoscope is between 0.25 and 0.75.

Analysis of the Secondary Outcome

For the secondary outcome, severe complications occurring between induction and 2 minutes following intubation, we will perform an unadjusted, intention-to-treat comparison of patients randomized to the video laryngoscope group versus patients randomized to the direct laryngoscope group, using a chi-square test.

Analyses of Exploratory Outcomes

For all pre-specified exploratory outcomes, we will conduct unadjusted, intention-to-treat analyses comparing patients randomized to the video laryngoscope group versus patients randomized to the direct laryngoscope group. We will calculate absolute risk differences or differences in medians between groups with the associated 95% confidence intervals.

Handling of Missing Data

We anticipate that no data on the primary outcome will be missing. When data are missing for the secondary or exploratory outcomes, we will perform complete-case analysis, excluding cases where the data for the analyzed outcome are missing. There will be no imputation of missing data for these outcomes. In adjusted analyses, missing data for covariates will be imputed using multiple imputations.

Trial status

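### Ventilator-free and ICU-free days are compared only by a difference in medians; a rank-based estimate beside it would register differences in ventilation or ICU time better

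*Protocol*

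**What the plan says.** The Protocol's Trial Summary lists "ICU-free days in the first 28 days Ventilator free days in the first 28 days" among the exploratory clinical outcomes, and section 7.2.3 lists the same two outcomes, in both places without a method. Protocol section 9.4.2 promises only "Intention-to-treat comparisons of secondary, exploratory, and safety outcomes; and" and names no estimator for them.

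The method is in the SAP under *Analyses of Exploratory Outcomes*: "For all pre-specified exploratory outcomes, we will conduct unadjusted, intention-to-treat analyses", followed by "We will calculate absolute risk differences or differences in medians between groups with the associated 95% confidence intervals". A risk difference suits a yes/no outcome, so the difference in medians is what remains for a count of days. The SAP names no rank test, ordinal model or mean difference for these outcomes, and no method for computing the CI of a median difference.

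Three further statements bear on the point:

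- On scoring, the SAP's *Data Collection* section says "Definitions for ICU-free days and ventilator-free days are provided in the supplementary file, sections 3 and 4". Those sections are not in the text available here.
- Death is a separate exploratory outcome, "28-day all-cause in-hospital mortality". As a binary outcome it receives an absolute risk difference with 95% CI.
- Under *Statistical Analysis Principles*, for analyses outside the primary, secondary and safety outcomes, "emphasis will be placed on the estimate of effect size with 95% confidence intervals". The same section provides descriptive summaries by group: mean and SD, or median and interquartile range.

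**The concern.** A free-day score usually combines death and duration on one scale with a ceiling of 28. If deaths score 0, the distribution has a lump at the bottom and most survivors sit near the top. The median reads that distribution at one point. If days are whole, the median moves in whole-day steps, and its interval often has a limit at exactly 0.

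For these outcomes the plan relies on the estimate and its interval. If the estimator hardly moves when the groups differ, the interval tells the reader little. The part at stake is time on the ventilator or in the ICU, because no other planned comparison covers it.

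**Working it through.** The documents give no effect size, spread, share at zero or power for free days, so there is no planned figure to reproduce. The check is a simulation.

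**Inputs from the documents**
- 1,000 patients per group, 1:1 (SAP, *Sample Size Estimation*).
- Score capped by a 28-day window.
- Between-group measure: difference in medians with 95% CI.

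**Assumed inputs**
- Deaths score 0.
- Ventilation time is lognormal, median 4 days, log-SD 1; score = 28 minus days ventilated, not below 0.
- Effect: ventilation time 20% shorter, so the median falls from 4 to 4 × 0.8 = 3.2 days, with mortality equal in both arms.
- CI for the median difference by percentile bootstrap; comparator a two-sided Wilcoxon/Mann-Whitney test at 0.05.
- 300 trials per scenario. The simulation error of a 30% result is √(0.3 × 0.7 / 300) ≈ 0.026, or about ±5 points at 95%.

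**Whole days, ventilation time 20% shorter, equal mortality**

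| Mortality, both arms | Median CI excludes 0 | Rank test detects |
|---|---|---|
| 30% | 31% | 74% |
| 35% | 22% | 57% |
| 40% | 25% | 52% |

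Repeat runs gave 24% against 64% (30% at zero) and 28–34% against 65–70%. Taken together, the ranges for mortality of 30–35% are 22–34% and 57–74%. In paired results the median CI registers the difference about 0.4 times as often: 31/74 = 0.42, 22/57 = 0.39, 24/64 = 0.38. One CI limit was exactly 0 in 17–55% of the trials tabulated above.

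**Dependence on the share at zero** (same effect, whole days)

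| Share at zero, both arms | 10% | 20% | 30% | 40% | 50% | 60% |
|---|---|---|---|---|---|---|
| Median CI excludes 0 | 44% | 31% | 24% | 24% | 1% | 0% |
| Rank test detects | 99% | 88% | 64% | 49% | 30% | 18% |

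At 60% both medians are 0 and the observed difference was 0 in every simulated trial. Below one half at zero the result is reduced sensitivity, not a guaranteed zero.

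**Fractional days.** For the same effect at mortality 30–40%, the median CI excluded 0 in 30–66% of trials and the rank test detected the difference in 47–71%. The direction is the same and the gap is smaller.

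**A mortality difference, for contrast.** Power of the separate risk difference, 30% against 25%, 1,000 per arm, two-sided 0.05:
- Null standard error: √(2 × 0.275 × 0.725 / 1000) = 0.01997.
- Alternative standard error: √((0.30 × 0.70 + 0.25 × 0.75) / 1000) = 0.01994.
- Power = Φ[(0.05 − 1.96 × 0.01997) / 0.01994] = Φ(0.545) ≈ 71%.

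The same formula gives 67% for 35% against 30% and 64% for 40% against 35%. A rank test on whole free days detected these 5-point differences in about 44–53% of trials. For a pure mortality effect, the planned risk difference is therefore already the more powerful comparison.

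**The case against.** The case on the other side is substantial, and most of it limits the size of the point.

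- **Mortality is covered.** A reader might infer that the trial could miss a difference in death. The documents do not support that: 28-day in-hospital mortality has its own risk difference and CI, with better power than a rank test on free days.
- **The distribution is assumed.** A reader might take a large mass at zero and whole-day counting as facts of the plan. The available text states neither. Whole-day counting drives much of the gap.
- **The effect is chosen for illustration.** The trial is designed for a 5-point gain in first-attempt success, and its effect on later outcomes may be small. For a mortality reduction of 1 point the rank test itself has only 6–7% power, and 12% at 2 points. A ventilation time 20% shorter is likewise a chosen effect. The figures compare two measures; they do not forecast what the trial will find.
- **Interval width.** With no effect and whole days, the simulated median CI excluded 0 in at most about 2% of trials, and a reader might infer that the planned intervals are too wide. That follows from the percentile bootstrap and whole-day scoring assumed here. The available SAP text specifies neither.
- **Role of the outcomes.** They are exploratory and meant for estimation. Counting how often an interval excludes 0 is a testing yardstick, used here only as a measure of sensitivity. Interquartile ranges by group, where reported, would show more than one point of the distribution. That an interval touching 0 would be read as no clinical effect is conjecture.
- **Interpretability.** Days are easier to understand than an odds ratio or a probability.

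What these objections leave standing: the median difference is the only between-group estimate planned for ventilation and ICU time, and it was less sensitive than the rank comparison in every scenario with an effect.

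**Conclusion.** The point holds as a minor improvement in precision. As written, the SAP compares the two free-day outcomes by a difference in medians alone. If deaths score 0 and days are whole, with 1,000 per arm, mortality of 30–35% and ventilation time 20% shorter, the interval excludes 0 in about 22–34% of trials against about 57–74% for a rank test. With fractional days the gap narrows but keeps its direction.

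The exact figures depend on the assumed lognormal distribution, the bootstrap interval and the effect chosen. ICU-free days were not simulated separately; the reasoning carries over if their distribution has a similar shape. The primary and secondary conclusions are unaffected.

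**What to change.** In the SAP, *Analyses of Exploratory Outcomes*, add one sentence: for ventilator-free and ICU-free days, a between-group estimate that uses the whole distribution will also be reported with its 95% CI. Name in advance which one, either the Mann-Whitney probability or the odds ratio from a proportional-odds model. Keep the medians, interquartile ranges and median difference so that readers still see a result in days.

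The cost is one sentence and one extra analysis per outcome, with no new data or patients and no change to the primary analysis. Both measures are less intuitive than days, and the odds ratio adds a proportional-odds assumption, which the Mann-Whitney probability avoids. Timing matters: Protocol section 9.4 labels analyses in the SAP as a priori and those requested after enrollment is complete as post hoc, so the sentence should go in before enrollment ends.
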